# 9.3. Reporting of Adverse Events and Serious Adverse Events

It is the responsibility of the Principal Investigator to determine the grade, attribution and expectedness of the event and if the event is reportable according to the requirements outlined in the protocol.

For this investigational agent the following criteria should be met to consider an adverse event reportable:

- The event occurred within 10 hours after the injection of the investigational agent, 

  11C-acetate.
- All unexpected events regardless of grade or attribution.
- Expected events that are grade 3 or higher.
- Expected events that are possibly, probably or defiantly related to the investigational agent.

When reporting please supply a narrative with as much description of the event as possible (chart note is acceptable) along with the completed AE Log or CRF signed and dated by the Principal Investigator.

The narrative should include:

Protocol number and name
Subject number
Date of onset
A detailed description of the event
If the study procedure was discontinued

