#### Risk/Benefit

#### C-Acetate

Participants will undergo one C-acetate scan in this study. C-acetate is a positron emitting radiopharmaceutical. As such, it poses an intrinsic radiation exposure risk. However, when administered in low tracer doses as a PET imaging agent, as described in this protocol, this risk is felt to be small. The organ and total body doses associated with C-acetate PET/CT imaging are felt to be comparable to those associated with other widely used clinical nuclear medicine procedures.

To date approximately 3,450 humans have been studied with C-acetate in published literature. There have been no reported AEs associated with the administration of C-acetate and no adverse reactions are expected as a result of the IV injection of C-acetate. We will continue to monitor this information as the study progresses, including reviewing current literature and our in-house monitoring of this study.

There is potential with intravenous injections, including C-Acetate, for allergic reactions. The dose will be delivered intravenously by skilled clinical professionals, and subjects will be monitored for any signs or symptoms of allergic reaction by trained personnel during the PET procedure. Symptoms of an allergic reaction could include itching, rashes, shortness of breath, low blood pressure or wheezing.

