### **Lumbar Puncture (Optional)**

Lumbar puncture (LP) may be associated with pain during the performance of the procedure. This is usually temporary and confined to the lower back. Headache may occur in about 5% of elderly people who undergo a LP. Less commonly, in about 1-4% of participants, a persistent low pressure headache may develop, probably due to a leakage of CSF. Lower rates of post-LP headaches have been noted in elderly patients. If a post-LP headaches persists it may need additional treatment, e.g. with fluids and analgesics. Uncommonly, a blood patch (injection of some of the participant's blood to patch the CSF leak) may be needed. Potential but rare risks of lumbar puncture include

infection, damage to nerves in the back, and bleeding into the CSF space. The risk of these is much less than 1%.

No psychological, social or legal risk is expected. While loss of confidentiality is possible, it is felt to be very unlikely due to the small number of professionals involved in the study with knowledge of this information. All clinicians and research staff involved are well trained in HIPAA practices.

There is no anticipated benefit to study subjects as a result of their participation in this study. There is a potential benefit to general society if C-acetate PET/CT proves to be a useful imaging agent for evaluating amyloid-induced neuroinflammation.

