- physician to determine if the MRI can be used for the purposes of the study, this may occur prior to consent and enrollment in this study.
- 6. Amyloid brain PET/CT scan (required for Cohort 1 and Cohort 3) In order to reduce costs, subjects may be recruited from other studies that perform amyloid PET/CT (typically using F-florbetaben or F-florbetapir. The CMS coverage with evidence development IDEAS amyloid PET/CT study starts recruitment February 2016, providing Medicare reimbursement for clinical amyloid PET/CT scans for the first time; Penn will be a site for this study and we anticipate that many patients being considered for this experimental C-Acetate imaging protocol will qualify to undergo clinical Amyloid PET/CT as part of the IDEAS registration trial (IRB 824052). Amyloid PET/CT scans should be completed within 6 months of study enrollment. If a subject has not undergone an Amyloid brain PET/CT as part of IDEAS or clinically then they will be asked to undergo a research Amyloid brain scan after they have consented for this study. If it is done as part of this research study the FDA approved radiotracer [18F]florbetaben (Neuraceq) will be used according to the standard Penn imaging procedure. For Cohort 1 and Cohort 3, the Amyloid brain PET/CT scan will be reviewed by an investigator or designee prior to scheduling the C-Acetate PET/CT scan, for subjects in Cohort 2 if an Amyloid PET is available it will be reviewed, however, it is not required for participation in Cohort 2.. If the Amyloid PET/CT scan is deemed to be negative then the subject will be considered non-evaluable and will be withdrawn from the study. Non-evaluable subjects will be replaced in the study enrollment total.

Baseline assessments: may be performed the same day as screening assessments or on a separate day within 90 days of the C-Acetate PET/CT, including the day of that study.

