### Optional: Cerebrospinal fluid (CSF) by Lumbar Puncture (LP).

Some subjects may be asked to undergo an optional lumbar puncture to collect CSF. If subjects agree to the LP it will be performed by a qualified physician who is experienced in performing the procedure. Subjects, or their designated decision maker, will call the investigator to report any adverse events associated with the LP procedure. Patients who have previously had CSF collected and stored or tested will not be asked to repeat these procedures. If it is being performed prior to the imaging, lumbar puncture should occur a minimum of 48 hours prior to the C-Acetate PET/CT scan.

The following additional patient data may be self-reported by the patient or obtained from medical chart review: demographics (including gender, date of birth and race).

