### 9.2. Recording of Adverse Events

At each study visit session, the Principal Investigator or designee, must seek information from the subject in reference to any adverse events specific to imaging procedures or injection of C-acetate that may have occurred by specific questioning and as appropriate by examination. Information on all adverse events should be recorded in as much detail as possible on a source document or the medical record and entered on the Adverse Event Log.

All adverse events occurring during the AE reporting period of 10 hours post C-acetate injection will be recorded. The clinical course of each event should be followed until resolution, stabilization, or until it has been determined that the study treatment or participation is not the cause. Serious adverse events that are still ongoing at the end of the study period must be followed up to determine the final outcome. Any serious adverse event that occurs after the study period and is considered to be possibly related to the study imaging or study participation should be recorded and reported immediately.

The PI should be contacted immediately to determine the reporting requirements for the event as outlined in the protocol.

The clinical course of each event should be followed until resolution, stabilization or until it has been determined that the investigational agent or study procedure is not the cause of the event.

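### The adverse-event window is defined inconsistently, and on one reading of the reporting criteria it leaves out harms of the optional research lumbar puncture

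*Combined protocol and SAP*

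**What the plan says.** Section 1.3 sets out the risks of the optional LP: "Headache may occur in about 5% of elderly people who undergo a LP", and "in about 1-4% of participants, a persistent low pressure headache may develop". It adds that a blood patch is uncommonly needed, and puts infection, nerve damage and bleeding at much less than 1%. For the tracer, the same section cites about 3,450 people without a reported AE and says that "no adverse reactions are expected as a result of the IV injection of" acetate.

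Section 6.1 makes LP timing conditional. If it is done before imaging, "lumbar puncture should occur a minimum of 48 hours prior to the" acetate scan. Subjects are to telephone the investigator about AEs after an LP. The calendar in section 6 marks LP under screening and baseline, and AE evaluation on the acetate day only.

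Section 9.1 runs the AE reporting period from the first study procedure to 10 hours after acetate. Section 9.2 describes the period as the 10 hours after acetate, and limits active questioning at each visit to "adverse events specific to imaging procedures or injection of" acetate. Sections 9.3 and 9.3.2 each list four criteria, beginning with "The event occurred within 10 hours after the injection of the investigational agent". The other three are unexpected events of any grade or attribution, expected events of grade 3 or higher, and expected events at least possibly related to the agent.

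**The concern.** The rules that staff would follow day to day (9.2, 9.3 and 9.3.2) are anchored to the acetate injection. The procedure for which the protocol itself predicts AEs is the LP, and an LP done before imaging comes at least two days earlier. Staff who follow the narrower sections would neither ask about an LP headache nor log one that began before the scan, while staff who follow 9.1 would log it. The same event could be handled differently from subject to subject.

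At stake is the safety record. A count of few or no AEs would partly reflect what was asked and when. A more serious LP event before the scan would depend on the investigator's reading of an ambiguous list before it reached the sponsor or the IRB.

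**Working it through.** The documents state no figure to reproduce, so the check is mainly a comparison of texts.

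**1. The windows side by side**

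| Place | Starts | Ends | Captures |
|---|---|---|---|
| 9.1, AE Reporting Period | first study procedure | 10 h after acetate | AEs to be reported |
| 9.2 | acetate injection | 10 h later | all AEs |
| 6.2 | not stated | 10 h after acetate | grade 3 or higher only |
| Section 6 calendar, note 7 | acetate injection | 10 h later | AE evaluation on acetate day |
| 9.3 and 9.3.2, first criterion | acetate injection | 10 h later | reportable events |

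There are two conflicts: the start of the period (9.1 against 9.2, 9.3 and 9.3.2) and the grade threshold for recording (6.2 against 9.2).

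**2. Timing of LP events**

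Count hours from the LP. With the shortest permitted gap before imaging, acetate is given at hour 48 and the window covers hours 48 to 48 + 10 = 58. An event starting in the first 48 hours falls before it. A longer gap moves the window later still. For an LP done more than 10 hours after acetate, every event falls after the window, and after the end of the 9.1 period too.

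**3. An LP headache under the four criteria**

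The four cannot all be required, because an event cannot be both expected and unexpected. Two readings remain. By the definition in 9.1 an LP headache is expected, since section 1.3 describes it, and it would not be attributed to acetate.

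- *Gate (10 hours plus one other criterion).* Any LP event before the injection is excluded, whatever its grade. Inside the window, an expected headache below grade 3 still fails the other three.
- *Alternatives (any one suffices).* Unexpected LP events and expected ones of grade 3 or higher are reportable. An expected event below grade 3 outside the window, such as a grade 2 persistent headache, meets none of the four.

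**4. Scale**

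The number of research LPs, n, is not given, so n = 5 and n = 10 are assumptions. With independent subjects, P(at least one) = 1 − (1 − p)^n.

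- Headache, p = 0.05: 1 − 0.95^5 = 0.226; 1 − 0.95^10 = 0.401.
- Persistent headache, p = 0.01 to 0.04: with n = 5, 0.049 to 0.185; with n = 10, 0.096 to 0.335.

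**5. Subjects who never receive acetate**

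Under section 6.1, if the amyloid scan is negative, "the subject will be considered non-evaluable and will be withdrawn from the study". Section 3 applies this to Cohort 1. Such a subject may already have had research florbetaben, and possibly an MRI or LP, yet a window anchored on acetate never opens. The enrolment ceiling of 30 less the 25 evaluable leaves room for at most 5 replacements.

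**The case against.** A reader might infer that LP must precede the scan and that its harms are therefore never reportable. The documents do not support this. The 48-hour rule applies only when the LP is done before imaging, and the calendar notes say that timing varies. Several provisions can reach LP events:

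- the 9.1 reporting period begins with the first study procedure, which includes a study LP;
- attribution in 9.1 is to a study treatment or procedure, and relatedness to the agent governs only the fourth criterion in 9.3;
- 9.1 treats an AE leading to hospitalization as serious, to be reported if judged related to participation;
- 9.2 requires immediate reporting of a serious event after the study period that is possibly related to participation;
- 9.3.2 lists further IRB triggers without a 10-hour limit;
- an event starting 48 to 58 hours after an LP can fall inside the window.

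Nor do subjects withdrawn after a negative amyloid scan escape questioning altogether: 9.2 requires questions about imaging AEs at every visit session. What they lack is a scheduled AE evaluation and any question about LP.

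The number of research LPs may also be small. LP is optional, subjects with earlier CSF are not asked to repeat it, and one source of controls is a study in which everyone has an LP. A new LP in all 25 evaluable subjects is implausible.

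These points stand, and they limit the claim. They do not remove the conflict between 9.1 and the later sections. The call-in arrangement is passive and is tied to neither the AE Log nor 9.3. The late serious-event rule covers neither events before the scan nor non-serious ones. The further IRB triggers generally depend on wider consequences than a single LP event.

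**Conclusion.** The point holds as an internal inconsistency with a practical consequence. The AE period has two incompatible starts, the recording threshold has two incompatible grades, and the 9.3 criteria lack a combining rule. Under the gate reading, LP harms before the scan are excluded from 9.3 and 9.3.2. Under the alternatives reading, the excluded group shrinks to expected LP events below grade 3 outside the window. The text does not settle which is meant. It does not show that LP harms have no reporting route.

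The size is modest: a 23% to 40% chance of at least one LP headache, if 5 to 10 research LPs are done and the protocol's 5% applies. This is the chance that a headache occurs, not that it is missed; some would begin inside the window or be telephoned in. The serious LP harms are far rarer. A correction is worthwhile because it is cheap and concerns the only procedure with AE rates above zero in the protocol.

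**What to change.** Amend the safety text as follows.

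- Align 9.2, 9.3, 9.3.2 and 6.2 with the 9.1 period, so that recording runs from the first study procedure to 10 hours after acetate, and settle whether all grades are recorded (9.2) or only grade 3 or higher (6.2).
- State in 9.3 and 9.3.2 how the criteria combine. Make unexpected, serious or grade 3 or higher events possibly related to a research procedure (LP, florbetaben or MRI) reportable without the acetate window.
- Add LP to the questioning in 9.2, and have the existing acetate-day evaluation ask about all events since consent.
- Link the LP telephone reports in 6.1 to the AE Log.
- Make one AE call to each subject who had a research procedure but was withdrawn before acetate, or whose LP followed the scan, and log what it finds.

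The cost is amendment wording, one added question at an existing visit, a handful of calls and a few more expected headaches on the AE Log. Low-grade expected headaches need only be logged. They need not trigger the 24-hour sponsor report or an IRB submission.

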# 9.3.1. Investigator Reporting: Notifying the Study Sponsor

All reportable Adverse Events and Serious Adverse Events must be reported to the study sponsor (The Department of Radiology, IND Support Office) by email within 24 hours of the event. Please include the AE Log and narrative as mentioned above.

If the event is considered serious the Principle Investigator must complete the Serious Adverse Event (SAE) form and fax or email to the study sponsor within 24 hours. All documentation will be kept on file at the study site.

Significant new information on ongoing adverse events should be provided promptly to the study sponsor

# 9.3.2. Investigator Reporting: Notifying the Penn IRB

This section describes the requirements for safety reporting by investigators who are Penn faculty, affiliated with a Penn research site, or otherwise responsible for safety reporting to the Penn IRB. The University of Pennsylvania IRB (Penn IRB)

requires expedited reporting of those events related to study participation that are unforeseen and indicate that participants or others are at increased risk of harm.

The Penn IRB requires Principal Investigators to submit AE and SAE reports within 10 working days from the time the investigator becomes aware of the event.

The Penn IRB will not acknowledge safety reports or bulk adverse event submissions that do not meet the criteria outlined below:

- The event occurred within 10 hours after the injection of the investigational agent.
- All unexpected events regardless of grade or attribution.
- Expected events that are grade 3 or higher.
- Expected events that are possibly, probably or defiantly related to the investigational agent.

# **Penn IRB Reporting Process**

Unanticipated problems posing risks to subjects or others as noted above will be reported to the Penn IRB using the form: "Unanticipated Problems Posing Risks to Subjects or Others Including Reportable Adverse Events" or as a written report of the event (including a description of the event with information regarding its fulfillment of the above criteria and follow-up/resolution).

Copies of each report and documentation of IRB notification and receipt will be kept in the Clinical Investigator's study file.

### Other Reportable Events to Penn IRB:

For clinical drug trials, the following events are also reportable to the Penn IRB:

- Any adverse event that would cause the sponsor to modify the investigators brochure, protocol or informed consent form, or would prompt other action by the IRB to assure protection of human subjects.
- Information that indicates a change to the risks or potential benefits of the research, in terms of severity or frequency. For example:
  - An interim analysis indicates that participants have a lower rate of response to treatment than initially expected.
  - Safety monitoring indicates that a particular side effect is more severe, or more frequent than initially expected.
  - A paper is published from another study that shows that an arm of your research study is of no therapeutic value.
- Change in FDA safety labeling or withdrawal from marketing of a drug, device, or biologic used in a research protocol.
- Breach of confidentiality
- Change to the protocol taken without prior IRB review to eliminate apparent immediate hazard to a research participant.
- Incarceration of a participant when the research was not previously approved under Subpart C and the investigator believes it is in the best interest of the subject to remain on the study.

- Complaint of a participant when the complaint indicates unexpected risks or the complaint cannot be resolved by the research team.
- Protocol violation (meaning an accidental or unintentional deviation from the IRB approved protocol) that in the opinion of the investigator placed one or more participants at increased risk, or affects the rights or welfare of subjects.

# 9.3.3. Sponsor Reporting

### Notifying the FDA

The study sponsor is required to report certain study events in an expedited fashion to the FDA. These written notifications of adverse events are referred to as IND Safety Reports. The following describes the safety reporting requirements by timeline for reporting and associated type of event:

# • Within 7 calendar days

Any study event that is:

- Associated with the use of the study drug.
- Unexpected.
- Fatal or life-threatening.

### Within 15 calendar days

Any study event that is:

- 1. associated with the use of the study drug,
- 2. unexpected, and
- 3. serious, but not fatal or life-threatening -OR-
- A previous adverse event that was not initially deemed reportable but is later found to fit the criteria for reporting (reporting within 15 calendar days from when event was deemed reportable).

Any finding from tests in laboratory animals that:

• Suggest a significant risk for human subjects including reports of mutagenicity, teratogenicity, or carcinogenicity.

## **Notifying Participating Investigators**

It is the responsibility of the study sponsor to notify all participating investigators, in a written IND safety report, of any adverse event associated with the use of the drug that is both serious and unexpected, as well as any finding from tests in laboratory animals that suggest a significant risk for human subjects. Additionally, sponsors are also required to identify in IND safety reports all previous reports concerning similar adverse events and to analyze the significance of the current event in light of the previous reports.

# **Additional Sponsor Reporting Requirements**

Sponsors are also required to identify in IND safety reports all previous reports concerning similar adverse events and to analyze the significance of the current event in light of the previous reports.

# 9.4. Medical Monitoring

It is the responsibility of the Principal Investigator, [name], to oversee the safety of the study. This safety monitoring will include careful assessment and appropriate reporting of adverse events as noted above, as well as the construction and implementation of a site data and safety-monitoring plan (see section 11 Auditing, Monitoring and Inspecting). Medical monitoring will include a regular assessment of the number and type of serious adverse events.

# 10. Data Handling and Record Keeping

# 10.1. Confidentiality

Information about study subjects will be kept confidential and managed according to the requirements of the Health Insurance Portability and Accountability Act of 1996 (HIPAA). Those regulations require a signed subject authorization informing the subject of the following:

- What protected health information (PHI) will be collected from subjects in this study
- Who will have access to that information and why
- Who will use or disclose that information
- The rights of a research subject to revoke their authorization for use of their PHI.

In the event that a subject revokes authorization to collect or use PHI, the investigator, by regulation, retains the ability to use all information collected prior to the revocation of subject authorization. For subjects that have revoked authorization to collect or use PHI, attempts should be made to obtain permission to collect at least vital status (i.e. that the subject is alive).

All research personnel associated with this study have completed the University of Pennsylvania human subjects training as well as HIPAA Compliance Training. Trained staff will assess eligibility, introduce the study rationale, procedures, study risks, and collect the combined informed consent/HIPAA authorization form. The study team will work to uphold the privacy of the participants in several ways. Communications made among study staff regarding participants will use ID numbers whenever possible and minimize the use of patient name or other identifying information except when necessary for conduct of the study. Paper-based records will be kept in a secure location and only be accessible to personnel involved in the study. Computer-based files will only be made available to personnel involved in the study through the use of access privileges and passwords. Whenever feasible, identifiers will be removed from study-related information. In data analysis sets, we will use ID numbers and/or patient initials only.

Precautions will be applied to protecting subject privacy and the protected health information detailed below:

